9.4.1.3.3. Conjunctivitis

For patients with treatment-related conjunctivitis <Grade 3, the investigator is advised to initiate symptomatic treatment and follow up observation of the event. If the severity increases to Grade ≥ 3 , or symptoms persists for >10 days after symptomatic treatment, the investigator is advised to refer the patient to an ophthalmologist for further evaluation and treatment.

9.4.1.3.4. Electrolyte Abnormalities

Consistent with observations with other EGFR mAbs, hypomagnesemia has been very commonly reported in patients treated with necitumumab in combination with cisplatin-based regimens. Hypomagnesemia is considered a class effect for EGFR mAbs. Monitor patients for hypomagnesemia, hypocalcemia, hypokalemia, and hypophosphatemia prior to each administration of necitumumab and after completion of necitumumab, until within normal limits. Prompt repletion is recommended, as appropriate.

9.4.1.3.5. Thromboembolic Events

In the Phase 3 study JFCC, there was an increase in VTEs and ATEs in the investigational arm (necitumumab in combination with gemcitabine and cisplatin) compared to the active control arm (gemcitabine and cisplatin). The relative risk of VTEs or ATEs was approximately 3-fold higher in patients with a reported history of VTEs or ATEs.

In Study JFCB (INSPIRE), which investigated necitumumab in combination with pemetrexed and cisplatin (PC+N) in patients with nonsquamous NSCLC, patients experienced an increased rate of serious thromboembolic events (including fatal events) in the PC+N Arm as compared to pemetrexed and cisplatin (PC) alone. Furthermore, the addition of necitumumab did not improve the efficacy outcome over PC alone in advanced nonsquamous NSCLC. Administration of necitumumab in combination with pemetrexed and cisplatin is not recommended.

Discontinuation of necitumumab in patients who experience a VTE or ATE should be considered after a thorough benefit-risk assessment for the individual patient.

9.4.1.3.6. Pneumonia and Sepsis

During the conduct of Study JFCL (JFCL; Phase 2 study to investigate carboplatin and soluble paclitaxel with or without necitumumab in patients with squamous NSCLC), following the non-blinded review of SAE cases that included reports related to pneumonia and sepsis, an imbalance in the number of SAEs, including fatal cases, for the necitumumab group compared with the paclitaxel-carboplatin group was found.

The early occurrence of a number of these cases may have indicated an issue regarding the enrollment of the appropriate patients. The sponsor had therefore provided clarification and reinforcement of the inclusion/exclusion criteria, requesting the investigator's particular attention with regard to infections and conditions predisposing to infections ongoing at the time of enrollment in a protocol amendment. During the further conduct of this trial, only single

additional reports were received, notably of cases reporting pneumonia and septic complications with concurrent neutropenia.

The review of the data from the Phase 3 study of necitumumab in combination with gemcitabine and cisplatin (JFCC; SQUIRE) did not show any evidence of an increased risk of serious lung infections or neutropenia associated with necitumumab in this combination.

9.4.1.3.7. Cardiorespiratory Disorders

An increased frequency of cardiorespiratory arrest or sudden death was observed with necitumumab. Cardiorespiratory arrest or sudden death was reported in the pivotal Study JFCC (SQUIRE) in 2.8% (15/538) of patients treated with necitumumab plus gemcitabine and cisplatin compared to 0.6% (3/541) of patients treated with chemotherapy alone. Twelve of the 15 patients died within 30 days of the last dose of necitumumab and had comorbid conditions, including history of chronic obstructive pulmonary disease (n=7), hypertension (n=5), hypomagnesemia (n=4), and coronary artery disease (n=3). Eleven of the 12 patients had an unwitnessed death.

9.4.2. Supportive Care Guidelines for Pembrolizumab

Patients should receive appropriate supportive care measures as deemed necessary by the treating investigator. Suggested supportive care measures for the management of AEs with potential immunologic etiology are outlined below. Where appropriate, these guidelines include the use of oral or intravenous treatment with corticosteroids as well as additional anti-inflammatory agents if symptoms do not improve with administration of corticosteroids. Note that several courses of steroid tapering may be necessary, as symptoms may worsen when the steroid dose is decreased. For each disorder, attempts should be made to rule out other causes, such as metastatic disease or bacterial or viral infection, which might require additional supportive care. The treatment guidelines are intended to be applied when the investigator determines the events to be related to pembrolizumab.

Note: if after the evaluation the event is determined not to be related, the investigator does not need to follow the treatment guidance (as outlined below). Refer to Section 9.4.1.2.1.1 for dose modification.

It may be necessary to perform conditional procedures such as bronchoscopy, endoscopy, or skin photography as part of evaluation of the event.

9.4.2.1. Immune-Mediated Pneumonitis

Patients who experience **Grade 2** events shall be treated with systemic corticosteroids. When symptoms improve to Grade 1 or less, steroid taper should be started and continued over at least 4 weeks.

Grade 3-4 events shall immediately be treated with intravenous steroids. Additional anti-inflammatory measures can be administered, as needed. Pembrolizumab shall be withheld for moderate (Grade 2) pneumonitis, and permanently discontinued pembrolizumab for severe (Grade 3) or life-threatening (Grade 4) pneumonitis.

Prophylactic antibiotics for opportunistic infections in the case of prolonged steroid administration shall be considered.

9.4.2.2. Type 1 Diabetes Mellitus (if new onset, including diabetic ketoacidosis [DKA]) or \geq Grade 3 Hyperglycemia, if associated with ketosis (ketonuria) or metabolic acidosis (DKA) or T1DM or Grade 3-4 Hyperglycemia

Insulin replacement therapy is recommended for type I diabetes mellitus and for Grade 3-4 hyperglycemia associated with metabolic acidosis or ketonuria.

Patients shall be evaluated with serum glucose and a metabolic panel, urine ketones, glycosylated hemoglobin, and C-peptide.

9.4.2.3. Immune-Mediated Hypophysitis

Grade 2 events shall be treated with corticosteroids. When symptoms improve to Grade 1 or less, steroid taper should be started and continued over no less than 4 weeks. Replacement of appropriate hormones may be required as the steroid dose is tapered.

Grade 3-4 events shall be treated with an initial dose of I.V. corticosteroids followed by oral corticosteroids. When symptoms improve to Grade 1 or less, steroid taper should be started and continued over at least 4 weeks. Replacement of appropriate hormones may be required as the steroid dose is tapered.

Pembrolizumab must be withheld for moderate (Grade 2) hypophysitis, withheld or discontinued for severe (Grade 3) hypophysitis, and permanently discontinued for life-threatening (Grade 4) hypophysitis.

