7.3.2. Discontinuation of Study Therapy

Patients will be discontinued from the study treatment in the following circumstances:

- Enrollment in any other clinical trial involving a study drug or enrollment in any other type of medical research judged not to be scientifically or medically compatible with this study.
- The patient, for any reason, requires treatment with another therapeutic agent that has been demonstrated to be effective for treatment of the study indication; discontinuation from study therapy occurs prior to introduction of the new agent.
- Investigator/Physician Decision
 - The investigator/physician decides that the patient should be withdrawn from the study due to an intercurrent illness or change in the patient's condition that renders the patient unsuitable for further treatment in the opinion of the investigator.

- Any study therapy-related event that is deemed life-threatening, regardless of grade, warrants discontinuation of that therapy and/or discontinuation from all therapy if appropriate in the opinion of the investigator.
- If the patient has progressive disease (PD, confirmed by irRECIST or unconfirmed but with clinically worsening/deterioration [Section 10.1.5.1 and Table JFCQ.10.1]).
- Any event(s) which would require a given study therapy to be modified by more than 2 dose reductions or to be held for more than 6 weeks following Day 1 of the most recent cycle warrants discontinuation of that therapy.
- The patient becomes pregnant during treatment.
- Patient Decision
 - The patient or patient's designee (for example, parents or legal guardian) requests to be withdrawn from the study or study treatment.
- Sponsor Decision
 - The sponsor stops the study or stops the patient's participation in the study for medical, safety, regulatory, or other reasons consistent with applicable laws, regulations, and good clinical practices (GCP).
- The patient is significantly noncompliant with study procedures and/or treatment.
- An unacceptable AE/toxicity (for example, a persistent moderate toxicity that is intolerable to the patient).
- A Grade 3 to 4 IRR, and potentially other drug-related AEs, as specified in Section 9.4.1 below.

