9.4.1.2. Dose Adjustments and Delays

9.4.1.2.1. Pembrolizumab

9.4.1.2.1.1. Pembrolizumab Dose Modifications

Adverse events (both nonserious and serious) associated with pembrolizumab exposure may represent an immunologic etiology. These AEs may occur shortly after the first dose or several

months after the last dose of treatment. Pembrolizumab must be withheld for drug-related toxicities and severe or life-threatening AEs as per [Table JFCQ.9.2](#).

Table JFCQ.9.2. Dose Modification Guides for Pembrolizumab Drug-Related Adverse Events

Toxicity	Hold Treatment For Grade	Timing for Restarting Treatment	Treatment Discontinuation
Diarrhea/Colitis	2-3	Toxicity resolves to Grade 0-1	Toxicity does not resolve within 12 weeks of last dose or inability to reduce corticosteroid to 10 mg or less of prednisone or equivalent per day within 12 weeks.
	4	Permanently discontinue	Permanently discontinue
AST, ALT, or Increased Bilirubin	2	Toxicity resolves to Grade 0-1	Toxicity does not resolve within 12 weeks of last dose.
	3-4	Permanently discontinue (see exception below) ^a	Permanently discontinue
Type 1 diabetes mellitus (if new onset) or Hyperglycemia	T1DM or 3-4	Hold pembrolizumab for new onset Type 1 diabetes mellitus or Grade 3-4 hyperglycemia associated with evidence of beta cell failure.	Resume pembrolizumab when patients are clinically and metabolically stable.
Hypophysitis	2-4	Toxicity resolves to Grade 0-1. Therapy with pembrolizumab can be continued while endocrine replacement therapy is instituted	Toxicity does not resolve within 12 weeks of last dose or inability to reduce corticosteroid to 10 mg or less of prednisone or equivalent per day within 12 weeks.
Hyperthyroidism	3	Toxicity resolves to Grade 0-1	Toxicity does not resolve within 12 weeks of last dose or inability to reduce corticosteroid to 10 mg or less of prednisone or equivalent per day within 12 weeks.
	4	Permanently discontinue	Permanently discontinue
Hypothyroidism		Therapy with pembrolizumab can be continued while thyroid replacement therapy is instituted	Therapy with pembrolizumab can be continued while thyroid replacement therapy is instituted.
Infusion Reaction	2 ^b	Toxicity resolves to Grade 0-1	Permanently discontinue if toxicity develops despite adequate premedication
	3-4	Permanently discontinue	Permanently discontinue

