Pneumonitis	2	Toxicity resolves to Grade 0-1	Toxicity does not resolve within 12 weeks of last dose or inability to reduce corticosteroid to 10 mg or less of prednisone or equivalent per day within 12 weeks.
	3-4	Permanently discontinue	Permanently discontinue
Renal Failure or Nephritis	2	Toxicity resolves to Grade 0-1	Toxicity does not resolve within 12 weeks of last dose or inability to reduce corticosteroid to 10 mg or less of prednisone or equivalent per day within 12 weeks.
	3-4	Permanently discontinue	Permanently discontinue
All Other Drug-Related Toxicity ^c	3	Toxicity resolves to Grade 0-1	Toxicity does not resolve within 12 weeks of last dose or inability to reduce corticosteroid to 10 mg or less of prednisone or equivalent per day within 12 weeks.
	4	Permanently discontinue	Permanently discontinue

Abbreviations: AE = adverse event; ALT = alanine aminotransferase; AST = aspartate aminotransferase; IRR = infusion-related reaction; T1DM = type 1 diabetes mellitus.

Note: Permanently discontinue for any severe or Grade 3 (Grade 2 for pneumonitis) drug-related AE that recurs or any life-threatening event.

- a For patients with liver metastasis who begin treatment with Grade 2 AST or ALT, if AST or ALT increases by greater than or equal to 50% relative to baseline and lasts for at least 1 week, then patients should be discontinued.
- b If symptoms resolve within one hour of stopping drug infusion, the infusion may be restarted at 50% of the original infusion rate (e.g., from 100 mL/hr to 50 mL/hr). Otherwise, dosing will be held until symptoms resolve and the patient should be given premedication for the next scheduled dose. Refer to [Table JFCQ.9.5 – IRR Treatment Guidelines](#) for further management details.
- c Patients with intolerable or persistent Grade 2 drug-related AE may hold study medication at physician discretion. Permanently discontinue study drug for persistent Grade 2 adverse reactions for which treatment with study drug has been held, that do not recover to Grade 0-1 within 12 weeks of the last dose.

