9.4.2.4. Immune-Mediated Hyperthyroidism or Hypothyroidism

Thyroid disorders can occur at any time during treatment. Patients shall be monitored for changes in thyroid function (at the start of treatment, periodically during treatment, and as indicated based on clinical evaluation) and for clinical signs and symptoms of thyroid disorders.

Grade 2 hyperthyroidism events (and **Grade 2-4** hypothyroidism):

In hyperthyroidism, non-selective beta-blockers (for example, propranolol) are suggested as initial therapy. Thyroid hormone replacement therapy, with levothyroxine or liothyronine, is indicated per standard of care. Isolated hypothyroidism may be managed without treatment interruption and without corticosteroids.

Grade 3-4 hyperthyroidism

Treatment with an initial dose of I.V. corticosteroid followed by oral corticosteroids is recommended. When symptoms improve to Grade 1 or less, steroid taper should be started and continued over no less than 4 weeks. Replacement of appropriate hormones may be required as the steroid dose is tapered.

Pembrolizumab must be withheld for severe (Grade 3) hyperthyroidism, and permanently discontinued for life-threatening (Grade 4) hyperthyroidism.

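### For Grade 4 hypophysitis, the row in Table JFCQ.9.2 lets pembrolizumab restart after recovery, while Protocol Section 9.4.2.3 requires it to be stopped for good

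*Protocol*

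**What the plan says.** Two parts of the protocol give a rule for pembrolizumab in Grade 4 hypophysitis.

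- **Section 9.4.2.3** (supportive care): withhold at Grade 2, withhold or discontinue at Grade 3, and at Grade 4 the drug must be "permanently discontinued for life-threatening (Grade 4) hypophysitis".
- **Table JFCQ.9.2** (Section 9.4.1.2.1.1, dose modification): one row, covering Grades 2-4, whose restart condition is "Toxicity resolves to Grade 0-1. Therapy with pembrolizumab can be continued while endocrine replacement therapy is instituted". The row's discontinuation column applies only if toxicity has not resolved within 12 weeks of the last dose, or prednisone (or equivalent) cannot be brought to 10 mg a day or less in that time. There is no separate Grade 4 line.

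Two general rules also apply. The note under the table reads "Permanently discontinue for any severe or Grade 3 (Grade 2 for pneumonitis) drug-related AE that recurs or any life-threatening event". Section 7.3.2 says "Any study therapy-related event that is deemed life-threatening, regardless of grade, warrants discontinuation of that therapy".

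Sites are directed to the table. Section 9.4.1.2.1.1 introduces it with "Pembrolizumab must be withheld for drug-related toxicities and severe or life-threatening AEs as per" and then names the table. Section 9.4.2 tells the reader "Refer to Section 9.4.1.2.1.1 for dose modification".

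**The concern.** The row and Section 9.4.2.3 name the same event and the same grade, and they give opposite answers on whether the patient may ever receive pembrolizumab again. They agree that dosing stops at onset. The conflict is about what happens after recovery.

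The protocol does not say which source prevails. Section 9.4.2 presents its measures as suggestions and refers to the table's section for dose modification, so a site could reasonably treat the table as controlling. A site that applies the row alone could re-expose a patient to pembrolizumab after a life-threatening immune reaction. The row would also be in use during continued access, where Section 8.1.2 lets treatment run until a Section 7.3 discontinuation criterion is met.

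**Working it through.** The plan states no figure to reproduce. The check is a comparison of texts, followed by a rough sizing.

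**1. Instruction for Grade 4 hypophysitis, by source**

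| Source | Instruction |
|---|---|
| Table JFCQ.9.2, hypophysitis row | Hold; restart at Grade 0-1; stop only on the 12-week criteria |
| Section 9.4.2.3 | Permanent discontinuation |
| Note under Table JFCQ.9.2 | Permanent discontinuation after any life-threatening event |
| Section 7.3.2 | Discontinuation warranted after a related life-threatening event |

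Section 9.4.2.3 equates Grade 4 with life-threatening, which is how the last two rules come to apply. The direct contradiction is between the first two lines.

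**2. The case on which they differ.** Take a patient with Grade 4 hypophysitis that resolves to Grade 0-1, with steroids down to the permitted dose, within 12 weeks. Under the row, pembrolizumab may restart. Under Section 9.4.2.3 it may not.

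**3. Grades 2 and 3.** Section 9.4.2.3 withholds at Grade 2 and offers withholding or discontinuation at Grade 3. Both fit the row, provided its sentence on endocrine replacement is read as applying once the hold criteria are met.

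**4. Is the row an outlier?** The table has 10 rows. Seven state their own permanent stop at Grade 4 or Grades 3-4: diarrhea/colitis, liver enzymes/bilirubin, hyperthyroidism, infusion reaction, pneumonitis, renal failure/nephritis, and all other drug-related toxicity. The three without one are type 1 diabetes/hyperglycemia, hypophysitis and hypothyroidism.

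The text requires a permanent stop at Grade 4 for five immune events:

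| Event | Text section | Table row agrees? |
|---|---|---|
| Pneumonitis | 9.4.2.1 | Yes |
| Hypophysitis | 9.4.2.3 | **No** |
| Hyperthyroidism | 9.4.2.4 | Yes |
| Nephritis | 9.4.2.6 | Yes |
| Colitis | 9.6.3 | Yes |

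Four of five match. Hyperthyroidism is the closest comparison: its text says "permanently discontinued for life-threatening (Grade 4) hyperthyroidism", and its table row has a separate Grade 4 line saying the same.

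**5. How often could it arise?** Planned enrolment (Protocol Synopsis) is Part A 3-12, Part B 54 and Part C 6-12.

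- Lower total: 3 + 54 + 6 = 63
- Upper total: 12 + 54 + 12 = 78

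The documents give no rate for Grade 4 hypophysitis, so a range of *p* = 0.1% to 1% is assumed. Expected cases are *np*, and the chance of at least one case is 1 − (1 − *p*)^*n*.

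| Assumed *p* | Expected cases, *n* = 63 to 78 | Chance of at least one case |
|---|---|---|
| 0.1% | 0.06 to 0.08 | 6.1% to 7.5% |
| 1% | 0.63 to 0.78 | 46.9% to 54.3% |

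These are chances that a case occurs. Wrongful rechallenge also needs recovery within the 12-week limits, a patient still on study, and a site that follows the row and overlooks the note and Section 9.4.2.3. It is therefore less likely, by an amount the documents do not allow one to estimate.

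**The case against.** The strongest reply is that the table already answers the question. Its own note requires a permanent stop after any life-threatening event, so a reader who takes the row and note together with Section 9.4.2.3 would stop. Section 9.4.2 also points to the whole of Section 9.4.1.2.1.1, note included. That is correct for a careful reader, and it limits the risk. It does not repair the row. Seven other rows state their own Grade 4 stop without relying on the note, so a row that names Grade 4 under hold-and-restart reads like a deliberate exception.

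Other points have some force:

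- **It may be deliberate.** All three rows lacking a Grade 4 stop concern conditions managed with hormone or insulin replacement. But Section 9.4.2.3 states the opposite rule for hypophysitis, and no rationale for a difference is given. If the row was intended, the text is wrong, and one of the two still has to change.
- **Hyperglycemia raises a related question.** Its row allows resumption after Grade 3-4 events, which sits uneasily with the note. Section 9.4.2.2 sets no discontinuation rule, however, so there is no direct clash between text and row as there is here.
- **Section 7.3.2 is weaker support.** It says discontinuation is warranted, not that it is permanent, and it goes on to leave stopping all therapy to the investigator's opinion. It supports stopping but is not a separate contradiction of equal weight.
- **The sponsor would probably know.** A life-threatening event is a serious adverse event reportable within 24 hours (Section 10.2.1.1), and the sponsor physician monitors safety throughout (Section 10.2.3). This makes an unnoticed rechallenge less likely but leaves the conflicting instruction in place.

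**Conclusion.** The concern holds. For Grade 4 hypophysitis the table row permits pembrolizumab to restart after recovery, and Section 9.4.2.3 forbids it. The table's note and Section 7.3.2 favour stopping without correcting the row. The four-of-five agreement elsewhere makes a drafting slip the likeliest explanation, though the documents cannot prove intent.

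The consequence is confined to patient safety. The analysis of overall response rate is unaffected, and any effect on the descriptive exposure and discontinuation tables is likely to be one patient or none. The sizing rests wholly on the assumed rate of 0.1% to 1%, and it bounds the chance of a case, not of a wrongful rechallenge. The event is rare, but the harm would be serious and the correction costs almost nothing, so it should be fixed.

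**What to change.** Let Section 9.4.2.3 stand and bring the table into line with it:

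1. Limit the hold-and-restart line of the hypophysitis row to Grades 2-3.
2. Add a separate Grade 4 line requiring permanent discontinuation, laid out as in the hyperthyroidism row.
3. State that continuing pembrolizumab on endocrine replacement applies only after the hold criteria have been met.

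The cost is one table row, in a protocol amendment or a clarification letter to sites. Sample size, visit schedule and analysis do not change.

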9.4.2.4. Immune-Mediated Hyperthyroidism or Hypothyroidism

Thyroid disorders can occur at any time during treatment. Patients shall be monitored for changes in thyroid function (at the start of treatment, periodically during treatment, and as indicated based on clinical evaluation) and for clinical signs and symptoms of thyroid disorders.

Grade 2 hyperthyroidism events (and **Grade 2-4** hypothyroidism):

In hyperthyroidism, non-selective beta-blockers (for example, propranolol) are suggested as initial therapy. Thyroid hormone replacement therapy, with levothyroxine or liothyronine, is indicated per standard of care. Isolated hypothyroidism may be managed without treatment interruption and without corticosteroids.

Grade 3-4 hyperthyroidism

Treatment with an initial dose of I.V. corticosteroid followed by oral corticosteroids is recommended. When symptoms improve to Grade 1 or less, steroid taper should be started and continued over no less than 4 weeks. Replacement of appropriate hormones may be required as the steroid dose is tapered.

Pembrolizumab must be withheld for severe (Grade 3) hyperthyroidism, and permanently discontinued for life-threatening (Grade 4) hyperthyroidism.

